#### **Sample Size Aim 2: Identify moderators and mediators of SEE Program effectiveness.**

The planned sample size (97 per trial arm) provides 80% power to detect *predictor* effects of the same magnitude as the anticipated treatment effect. For the *moderator* analysis, by oversampling African Americans to comprise 25% of the study population, we are powered to detect an increase of the R^2 by 4 percentage points (e.g., if the SEE program vs enhanced standard of care improves mean adherence from 60% to 70% in Whites and from 50% to 75% in African Americans, then the R^2 increase is 4%). For the *mediator* analysis, using the function wp.mediation (R package WebPower), the planned sample size provides 80% power to detect mediation when the standardized difference between the mean of the mediator in the treatment group and the mean in the control group is 0.6 standard deviations with a partial correlation of the mediator and medication adherence of 0.25.

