## METHODS

### **Specific Aim 1: Compare the efficacy of the SEE Program with enhanced standard care in improving glaucoma medication adherence.**

In Aim 1, we will test the efficacy of the SEE Program to improve medication adherence among glaucoma patients. Our study design is a randomized controlled clinical efficacy trial with an embedded mixed methods analysis. The primary outcome, medication adherence at six months, will be assessed objectively with electronic monitoring. We will test the efficacy of the intervention on improving medication adherence behavior while gathering data that will inform future program dissemination and implementation. We will conduct a parallel, two-armed RCT, recruiting participants (n=230) with self-reported poor adherence in equal numbers from two southeastern Michigan-based health systems {University of Michigan (UM) and Henry Ford (HF)}; that both serve low-income, minority populations. We will oversample African Americans to comprise at least 25% of our sample to ensure adequate power to assess improvements in this sub-population. We will enroll up to 160 participants at UM or HF. We will stop enrollment when the goal of 230 is met combining UM and HF.

We chose to work in two health systems to ensure adequate recruitment of patients who are poorly adherent to their medication and willing to participate.

The study will evaluate whether increasing glaucoma self-management support by having trained health educators provide MI-based counseling and personalized education, facilitated by an eHealth tool, improves medication adherence. We will use mixed methods (i.e., the collection, analysis, and combining of both quantitative and qualitative data) to investigate

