**Specific Aim: 2 Identify moderators and mediators of SEE Program effectiveness.**

The primary moderator we will assess is income (below the federal poverty line or not). We will also assess whether race (African American or not) and sex (male or female) moderate (interact with) the effect of the SEE Program on medication adherence. The primary moderator of treatment effect (income) will be assessed with an interaction term added to a linear regression model of continuous medication adherence, adjusted for known confounders of adherence.

**Specific Aim 3: Optimize the SEE Program for clinical dissemination using a mixed-methods evaluation of barriers and facilitators to implementation.**

In Aim 3, we will gain an in-depth understanding of participant experience in the SEE Program and of health system key stakeholders’ opinions on barriers and facilitators to implementation. Together, Aims 2 and 3 will give us a quantitative and qualitative evaluation of the SEE Program that will enable future program optimization through improved tailoring, more efficient protocols and opportunities to streamline the intervention. At the completion of these Aims, we will have developed a tool kit of all training and intervention materials to guide dissemination efforts in implementing better self-management support to improve glaucoma outcomes.

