### Exclusion criteria:

Do not speak English

Have a diagnose serious mental illness (defined as schizophrenia, bipolar disorder, or a major depressive episode with psychotic features)

Diagnosed cognitive impairment

Do not instill their own eye drops

Had laser or incisional glaucoma surgery within the last 3 months or scheduled during the six-month study period

Prisoners

Active uveitis or ocular infection

Participated in pilot study

Unable to attend all study visits

\*We will recruit men and women equally. We will oversample African American patients to ensure at least 25% representation in the trial sample.

UM Study staff will become registered Henry Ford Health Systems volunteers. Henry Ford staff will become registered as UM volunteers. This will allow for staff to access clinic space and electronic health records at each institution.

At UM and HF, research associates will call potential participants and obtain verbal consent to give a survey assessing self-reported medication adherence to determine study eligibility. Self-reported medication adherence will be measured from a single question asking “Over the past month, what percentage of your drops do you think you took correctly?” Those who self-report <85% adherence will be invited to participate in the study. Research associates will schedule a baseline visit to complete the informed consent process, the baseline survey, measurement of intraocular pressure and measurement of visual acuity and visual fields if participants have not had a reliable test with the last year(HVF SITA 24-2, ≤20% fixation losses, ≤15% false positives).

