### **Sample Size Aim 1: Compare the efficacy of the SEE Program with enhanced standard care in improving glaucoma medication adherence.**

We conducted brief interviews with 25 glaucoma specialists from throughout the US to gauge expert opinion regarding clinically important effect size. Their average recommendation for difference of group proportions of good adherence was 18.5 percentage points (95% CI 15.6-

21.5). Their average recommendation for difference of group mean adherence was 17.7 percentage points (95% CI 14.6-20.8). Additionally, mean medication adherence increased by 20 percentage points in our SEE Program pilot study from 65.7% ( $\pm 10.3$ ) at baseline to 85.7% ( $\pm 11.8$ ) after the program. With 97 participants in each group, a t-test has 80% power to detect a difference of 8 percentage points in mean adherence between the two groups, if the within group standard deviation (SD) is 20 ( $0.40 \times 20 = 8$ ). In our preliminary data the SD was 18, but we anticipate and plan for a possibly more diverse study group (calculated using R 'pwr' package). Our glaucoma specialists were divided on the importance of clinically important effect size, so we plan to be adequately powered for both continuous and binary adherence measures. Their average recommendation for difference of group proportions of good adherence was 18.5 percentage points (95% CI 15.6-21.5). The proposed sample size (n=97 per group) provides 80% power (at two-sided  $\alpha=0.05$ ) for Pearson's Chi Square Test of Independence to find a difference of 20 percentage points for the proportion of patients attaining good ( $\geq 80\%$ ) adherence between the intervention and control groups.

For our secondary outcome, with this sample size, we can detect a 1.1-point difference in mean change in Glaucoma Related Distress (scale 6-18) between trial arms if the SD is 2.8, as it was in our preliminary data. For this sample size in our exploratory outcome, we can detect a 1.9 mmHg difference in mean change in IOP between trial arms if the SD is 4.6 mmHg, as it was in our preliminary data. Although we will make concerted efforts to maximize retention, we will prepare for up to a 20% loss to follow-up as was experienced in our preliminary study and will enroll 115 participants in each arm for a total of 230 participants.

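### The Aim 2 race-moderator example is printed as a 4% R-squared increase but gives about 2.3% at the planning SD of 20 (2.8% at SD 18), with about 61% (71%) power at 97 per arm

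*Combined protocol and SAP*

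**What the plan says.** The section on sample size for Aim 2 says that, with African American participants making up 25% of the sample, the trial is powered to detect a 4-percentage-point increase in R-squared in the moderator analysis. It gives one example, in which the program "improves mean adherence from 60% to 70% in Whites and from 50% to 75% in African Americans", and states that the R-squared increase is then 4%. It gives no SD. The section opens from the Aim 1 sample size: "The planned sample size (97 per trial arm) provides 80% power to detect" predictor effects as large as the anticipated treatment effect.

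The section on sample size for Aim 1 computes power for mean adherence "if the within group standard deviation (SD) is 20", and adds "In our preliminary data the SD was 18". It also reports pilot spreads of ±10.3 at baseline and ±11.8 after the program.

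The 25% share is a minimum. Under Methods, Specific Aim 1: "We will oversample African Americans to comprise at least 25% of our sample". The note under the exclusion criteria likewise aims "to ensure at least 25% representation in the trial sample". Under Methods, Specific Aim 2, income is the primary moderator and race a further one. The interaction model described there is a linear regression of continuous adherence, "adjusted for known confounders of adherence".

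**The concern.** An R-squared increase means little to a clinical reader, so the example carries the message. It presents a 15-point race difference in program effect (25 minus 10) as sitting at the detectable threshold. The four means, the 25% share and equal allocation fix everything except the SD. At either SD that the document gives for adherence in its power calculation, the result falls well short of 4%.

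Assessing the race interaction is a stated aim, and the oversampling is justified by power in this subgroup. If the example overstates sensitivity, a non-significant interaction could be taken as evidence of similar benefit when the trial had a substantial chance of missing a 15-point difference.

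**Working it through.** **Inputs.** From the Aim 2 sample size section: means of 60 and 70 (White, control and SEE) and 50 and 75 (African American, control and SEE); African American share q = 0.25; 97 per arm, so N = 194. From the Aim 1 sample size section: equal arms, so p = 0.5; within-group SD 20 for planning and 18 in preliminary data; two-sided alpha 0.05. Carrying the SDs and alpha over to Aim 2 is an assumption; the outcome and the number per arm are the same.

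**Step 1. The general threshold.** If the full model's R-squared is itself 4%, f² = 0.04/0.96 = 0.0417 and the noncentrality is 194 × 0.0417 = 8.08. The F test with 1 and 190 df then has 80.8% power. If the full-model R-squared is 15%, power is 85.2%. The plan's threshold reproduces.

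**Step 2. The example's R-squared increase.**

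- Interaction: (75 − 50) − (70 − 60) = 15 points.
- Interaction variance: p(1−p) × q(1−q) × 15² = 0.25 × 0.1875 × 225 = 10.55.
- Overall mean: 0.375 × 60 + 0.375 × 70 + 0.125 × 50 + 0.125 × 75 = 64.375.
- Between-cell variance: 0.375 × (19.14 + 31.64) + 0.125 × (206.64 + 112.89) = 58.98.
- R-squared increase = 10.55 / (SD² + 58.98).

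| Within-cell SD | Calculation | R-squared increase |
|---|---|---|
| 20 (planning) | 10.55 / 458.98 | 2.30% |
| 18 (preliminary) | 10.55 / 382.98 | 2.75% |
| 14.3 (not in the document) | 10.55 / 263.5 | 4.0% |
| 11.8 (pilot, read as an SD) | 10.55 / 198.2 | 5.3% |
| 10.3 (pilot, read as an SD) | 10.55 / 165.1 | 6.4% |

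Anything that rounds to 4% needs an SD between about 13.2 and 15.6. No SD in the document lies there.

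**Step 3. Other readings.**

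- Partial R-squared, 10.55 / (SD² + 10.55): 2.57% at SD 20, 3.15% at SD 18.
- SD read as the total SD, 10.55 / SD²: 2.64% and 3.26%.
- A share above the 25% floor: the largest increase over all shares is 2.87% at SD 20 (share 47%) and 3.40% at SD 18 (share 46%).

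**Step 4. Power for the 15-point interaction.** This uses the noncentral F test with 1 and N − 4 df, noncentrality N × 10.55 / SD², and no covariates.

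| Analysed | SD 20 | SD 18 |
|---|---|---|
| 184 (230 less 20%) | 59% | 68% |
| 194 | 61% | 71% |
| 230 | 69% | 78% |

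A 20,000-run simulation at N = 194 gave 61.3% and 70.3%. At SD 20 with 194 analysed, a 30% or 40% share raises power to 66% or 72%.

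**Step 5. What would be detectable.** With 194 analysed and a 25% share, 80% power needs an interaction of about 18.7 points at SD 20 or 16.8 at SD 18. A 4% increase at SD 20 needs about 20.1 points. For the 15-point interaction, 80% power needs about 300 analysed at SD 20 or 243 at SD 18.

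**The case against.** The strongest objection is that one combined reading nearly recovers the printed figure. Take 18 as the overall SD and 4% as a partial R-squared or f². Residual variance is then 324 − 58.98 = 265.0, partial R-squared is 10.55 / 275.6 = 3.83%, f² is 10.55 / 265.0 = 3.98%, and power at 194 is about 79%. This may be how the example arose. But it departs from the text twice. The section speaks of the increase in R-squared, which on that reading is 10.55 / 324 = 3.26%. The value of 18 is also introduced by contrast with a within-group SD of 20, so within-group is its natural meaning. At SD 20 the same reading gives only 3.0% to 3.1% and 68% power.

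It is also fair that the Aim 2 section states no SD, and that the spreads elsewhere in the document give values on both sides of 4%. The pilot spreads overshoot it, however, and the plan did not use them for Aim 1.

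Finally, the planned confounder adjustment could raise power. To reach 80% for 15 points with 194 analysed, the residual SD must fall to 16.06. That means removing 1 − 16.06²/400, about 36% of the residual variance, from SD 20, or about 20% from SD 18. The document gives no such figure. Adjustment also leaves total outcome variance unchanged, so it would not be expected to bring the R-squared increase to 4%.

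What stands is the limit on scope: the general threshold is correct, race is not the primary moderator, and the trial's size comes from Aim 1.

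**Conclusion.** The concern holds. As written, the example gives an R-squared increase of about 2.3% at the planning SD of 20, or 2.8% at SD 18, not 4%. Unadjusted power for its 15-point interaction is about 61% or 71% with 97 per arm, so at SD 20 a true difference of that size would be missed about 39% of the time.

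This rests on carrying the Aim 1 SDs over to Aim 2, a 25% African American share, equal arms, two-sided alpha 0.05 and a model without covariates. The error is confined to the justification of a secondary aim, but it should be corrected because the plan offers no other moderator power statement in adherence points.

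**What to change.** State the SD behind the Aim 2 calculation, and say whether 4% is an increase in R-squared, a partial R-squared or f². Then do one of the following:

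- Keep the example and report it as an R-squared increase of about 2.3% with about 61% power at SD 20 and 194 analysed.
- Replace it with one that fits the threshold. Keeping the White means and the African American control mean of 50%, an African American intervention mean of 80% gives a 20-point interaction. Its variance is 0.25 × 0.1875 × 400 = 18.75 and the between-cell variance is 75, so the increase is 18.75 / 475 = 3.95% at SD 20, with about 85% power at 194.

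If the authors rely on confounder adjustment, they should state the share of variance they expect it to explain.

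Optionally, give the detectable interaction for income, the primary moderator. The document gives no poverty prevalence; under assumed values of 10%, 15% or 20%, it is about 27, 23 or 20 points at SD 20 with 194 analysed.

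The cost is protocol wording only. The Aim 2 power statement becomes less favourable; the primary sample size and analysis do not change.

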#### **DATA AND SAFETY MONITORING PLAN**

The study epidemiologist will lead the study team in quarterly review of study recruitment, adverse events, and compliance with the protocol. The study epidemiologist will work with the study statistician to prepare reports of recruitment, retention, and adverse events for the entire team.

We will follow the standard IRBMED AE/ORIO reporting plan.

Intraocular pressure will be measured at the baseline and exit study visits. If the IOP is more than 4mm Hg above the target pressure set by their ophthalmologist or, if no target pressure is set,  $>21$  mmHg, the participant will be walked over to the eye clinic for further evaluation. The

research associate will email the participant's ophthalmologist, and [name] (for UM participants) and [name] (for HFHS participants) to let them know what transpired and will also send them the note from the study visit and clinic visit through the electronic health record to determine appropriate follow up. If the participant's IOP is above the target but below the threshold for immediate clinical attention, the research associate will email the participant's ophthalmologist, and cc either [name] or [name] in addition to sending a notification to the ophthalmologist through the electronic health record to determine the appropriate follow up interval. The research associate will keep a log of all participants whose eye pressure met criteria to be walked to clinic to be reviewed during the quarterly reports.

#### **SECONDARY SITE**

University of Michigan will have a contract in place with Henry Ford Health Systems in place prior to beginning any study activities.
